8.2.3. Corneal events (GSK scale)

Following discussions with regulatory agencies, GSK developed a grading scale to capture both corneal examination findings and visual acuity changes in participants treated with GSK2857916. This GSK scale differs from the CTCAE criteria for eye disorders which relies mainly on patient's symptoms and patient's ability to attend to 'activities of daily living' for grading of events. Details of derivation this GSK scale based on corneal findings and visual acuity Ophthalmic Exam (collected from Ocular

form) can be found in Appendix 9 Table 22 and Table 23 of study protocol (Version: GSK Document Number [TMF-13990464](#)).

In addition to the listing, the following outputs will be provided for corneal events graded using the GSK scale:

1. Overview for corneal event (GSK scale)
2. Summary of grade of GSK scale
 - a. Summary of characteristics of corneal events (GSK scale) including the percentage of duration of exposure (see Section 15.6.2 for definition) with corneal events (GSK scale) of grade ≥ 2 and grade ≥ 3 respectively
 - b. Summary of onset time and duration of the first occurrence of corneal event (GSK scale) of a) grade 2 or above; 2) grade 3 or above.
3. Summary of actions taken with study treatment (e.g. dose reduction/delay/permanent discontinuation)
4. Summary of time to re-initiation of study treatment post treatment delay due to corneal events (GSK scale)
5. Change in grade of corneal events (GSK scale) from EOT to last follow-up
6. Summary of worst post-baseline corneal events (GSK scale)
7. Summary of worst post-baseline corneal events (GSK scale) by best response (PR or better vs. otherwise)
8. Summary of resolution (improve to grade 1 or better) in corneal events (GSK scale) during Follow-up period (from EOT visit to last follow-up visit).
9. Logistic regression analysis will be performed to explore possible risk factors for developing corneal Events (GSK scale ≥ 2). In addition to dose arm (3.4 mg/kg vs 2.5 mg/kg), Sex (Male vs Female), Age Group (< 65 vs. ≥ 65 years), Race (White, Other), the following risk factors will also be considered:
 - a. History of intraocular surgery: (Yes vs. No)
 - b. Lens status (pseudophakia vs natural lens) at baseline
 - c. Known history of dry eye per screening questionnaire (Presence vs. Absence)
 - d. Presence of keratopathy at baseline exam (None vs. Mild vs. Moderate/Severe)

Covariates will be selected using stepwise variable selection with entry and exit criteria of $\alpha=0.05$.
10. Summary of Blurred Vision and Dry Eye Events versus GSK Scale.
11. Summary of Ocular Symptoms and Visual Acuity Change (GSK Scale) by Worst Grade of Keratopathy
12. Summary of Ocular Symptoms and Visual Acuity Change (GSK Scale) by Worst Grade of Corneal Events (GSK Scale)
13. Summary of Ocular Symptoms and Visual Acuity Change (≥ 2 lines in Better Eye) by Worst Grade of Corneal Exam Finding
14. Summary of Eye Disorder Events (CTCAE) Leading to Dose Delays by Preferred Term and Maximum Grade.
15. Summary of Subjects with Dose Delay due to Eye Disorder Events (CTCAE) at the Time of Data Cutoff

16. Summary of Vision Blurred, and Dry Eye by Preferred Term in Subjects with Keratopathy
17. Summary of Vision Blurred, and Dry Eye by Preferred Term and Maximum Grade in Subjects with Keratopathy
18. Summary of Ocular Symptoms (CTCAE) by Preferred Term and Maximum Grade in Subjects with Keratopathy
19. Summary of Ocular Symptoms (CTCAE) by Preferred Term and Maximum Grade
20. Summary of Blurred Vision and Dry Eye Events versus Keratopathy
21. Summary of Ocular Symptoms (CTCAE) versus Keratopathy
22. Summary of Duration of Keratopathy with Concurrent Blurred Vision or Dry Eye
23. Summary of Duration of Keratopathy with Concurrent Ocular Symptoms (CTCAE)
24. Summary of GSK scale Events Characteristics II
25. Summary of Corneal Exam Finding (GSK scale) Characteristics II
26. Summary of Visual Acuity Change (GSK scale) Characteristics II
27. Summary of Maximum Grade for Corneal Exam Finding (GSK scale)
28. Summary of Maximum Grade for Visual Change (GSK scale)
29. Summary of Worsening in Best Corrected Visual Acuity (BCVA) Score (logMAR Score) Characteristics II
30. Summary of Blurred Vision and Dry Eye Event Characteristics II in Subjects with Keratopathy
31. Summary of Ocular Symptoms (CTCAE) Event Characteristics II in Subjects with Keratopathy
32. Summary of Unilateral Worsening in Best Corrected Visual Acuity (BCVA) to 20/50 or Worse Characteristics II
33. Summary of Bilateral Worsening in Best Corrected Visual Acuity (BCVA) to 20/50 or Worse Characteristics II
34. Summary of Unilateral Worsening in Best Corrected Visual Acuity (BCVA) to 20/200 or Worse Characteristics II
35. Summary of Bilateral Worsening in Best Corrected Visual Acuity (BCVA) to 20/200 or Worse Characteristics II
36. Percentage of Subjects with Blurred Vision/Dry Eye Event Associated with Worsening in Best Corrected Visual Acuity (BCVA) to 20/50 or Worse
37. Percentage of Subjects with Ocular Symptoms (CTCAE) Associated with Worsening in Best Corrected Visual Acuity (BCVA) to 20/50 or Worse
38. Update of Resolution Status for Unresolved Corneal Exam Finding
39. Update of Resolution Status for Unresolved Corneal Exam Finding Patients with Interview Clinical data
40. Update of Resolution Status for Unresolved Worsening in Best Corrected Visual Acuity (BCVA) Score (logMAR Score)
41. Update of Resolution Status for Unresolved Blurred Vision and Dry Eye Events in Subjects with Keratopathy
42. Update of Resolution Status for Unresolved Ocular Symptoms (CTCAE) in Subjects with Keratopathy
43. Summary of Worst Post-baseline Change in Best Corrected Visual Acuity (BCVA)

44. Summary of Worsening in Best Corrected Visual Acuity (BCVA) Score (logMAR Score ≥ 0.12) Characteristics II
45. Update of Resolution Status for Unresolved Worsening in Best Corrected Visual Acuity (BCVA) Score (logMAR Score ≥ 0.12)
46. Summary of Vision Blurred by Preferred term and Best Response Based on Independent Review Committee
47. Summary of Dry Eye by Preferred term and Best Response Based on Independent Review Committee
48. Summary of Vision Blurred by Maximum Grade, and Best Response Based on Independent Review Committee
49. Summary of Dry Eye by Maximum Grade, and Best Response Based on Independent Review Committee
50. Summary of Best Corrected Visual Acuity (BCVA) Score (Snellen Score) at Baseline Compared to 20/50
51. Worsening in Best Corrected Visual Acuity (BCVA) Score (logMAR Score) Excluding Subjects with Follow-up Shorter Than 80 Days
52. Summary of worst-case post baseline shift from baseline by BCVA categories
53. Summary of Worst-case Post Baseline Change from Baseline in Best Corrected Visual Acuity (BCVA) Score (logMAR score)
54. Summary of Worst-case Post Baseline Change from Baseline in Best Corrected Visual Acuity (BCVA) Score (logMAR score) in Subjects with Worsening to 20/50 or Worse in the Better Eye
55. Summary of Worst-case Post Baseline Change from Baseline in Best Corrected Visual Acuity (BCVA) Score (logMAR score) in Subjects with Worsening to 20/50 or Worse in at Least One Eye but not the Better Eye
56. Summary of Characteristics II for Keratopathy
57. Summary of Dose Modifications for Subjects with Keratopathy
58. Summary of Maximum Grade for Corneal Events (GSK scale)
59. Summary of Time from Onset of Last Occurrence to Last Exam in Subjects Who Did Not Recover from Grade 2 or Higher Corneal Exam Finding (GSK Scale) When Follow Up Ended
60. Summary of Ocular Symptoms by Preferred Term and Maximum Grade in Subjects with Worst Grade of Corneal Exam Findings (GSK scale) =1
61. Summary of Duration of Exposure since Re-start after First Dose Delay Due to Eye Disorder Events (CTCAE)
62. Summary of Corneal Events (GSK Scale) Occurrences After Dose Reduction to 1.92 mg/kg
63. Summary of Characteristics II for the Event of Giving up Driving due to Eyesight
64. Summary of Characteristics II for the Event of Giving up Reading due to Eyesight
65. Listing of Resolution in Grade of Corneal Events (GSK Scale) for each Corneal Event in patients experiencing >1 event
66. Listing of BCVA for patients who gave up driving due to eyesight
67. Listing of BCVA for patients who experienced difficulty reading newspapers due to eyesight
68. Bar Chart of Grade of Corneal Exam Finding by Cycle

69. Plot of Time to Recovery Post Treatment Discontinuation for Corneal Exam Findings
70. Plot of Time to Recovery Post Treatment Discontinuation for Keratopathy
71. Profile plot of patients with maximum corneal toxicity grade will be provided.
72. Plot of Visual Acuity and Corneal Finding Grade for subjects experiencing >1 Corneal Event (GSK Scale) for 2.5 mg/kg arm will be produced.

Details of the planned displays are provided in [Appendix 13](#): List of Data Display.

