3.1.1.1. Operating Characteristics of the Stopping Rules for Futility

The following assumptions were made in the estimation of the required sample size:

- Normal approximation of binomial proportion
- A response rate of $\geq 33\%$ in the BCMA arm and $\leq 15\%$ for the historical control
- A 1.25%, one-sided risk of erroneously claiming superiority of the BCMA arm, in the presence of no true underlying improvement
- A $\sim 90\%$ chance of rejecting the null hypothesis when the alternative hypothesis is true

An IA after approximately 38% of information is available (i.e., approximately after 25 participants out of originally planned 65 participants per arm are evaluable for IA), with a futility rule based on a gamma spending function.

The operating characteristics were refined using simulation to account for the within arm futility rule and the comparative futility rule. Based on the simulation results with the originally planned sample size of 65 participants per arm, there is 86.90% power to reject the null hypothesis within each arm with a 1-sided type I error of 1.23%.

Due to over enrolment, it is estimated that approximately 200 participants (~ 100 per arm) will be randomized to the frozen liquid solution. At the primary analysis, the null hypothesis will be rejected if the lower bound of 2-sided 97.5% exact C.I. exceeds the historical control rate of 15%.

With no change to the planned IA (i.e., approximately after 25 participants/arm are evaluable for IA, and same futility boundary), simulation results show that there is 92.38% power to reject the null hypothesis within each arm with a 1-sided type I error of 0.97% for 100 participants per arm as shown in [Table 1](#).

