3.1030	Full Safety	AE6	Summary of Cumulative Incidence of Infusion-Related Reactions by PT and Number of Doses Received at First Occurrence	Only PT term, no SOC needed. The number of doses received at first occurrence will be <= 1, <= 2, <= 4, <= 6, <= 8, <= 10, and Any	SAC [1], SAC [2]
3.1210	Full Safety	Mock-up SAFE_T1a	Summary of Cumulative Incidence of Corneal Events (GSK Scale) by Grade and Number of Doses Received at First Occurrence		SAC [1], SAC [2]
3.12030	Full Safety	ESI2b	Summary of Blurred Vision and Dry Eye Events versus GSK Scale		SAC [2]
3.1280	Safety	Mock-up SAFE_T5	Logistic Regression Analysis of Possible Risk Factors for Developing Corneal Events Grade >=2 (GSK Scale)	See Section 8.2.2 Item 9 for details.	SAC [1], SAC [2]
3.1290	Full Safety	Mock-up SAFE_T11	Summary of Thrombocytopenia and Bleeding Event		SAC [1], SAC [2]

CONFIDENTIAL

205678

Safety: Tables					
No.	Population	IDSL / Example Shell	Title	Programming Notes	Deliverable [Priority]
3.1246 1	Full Safety	OAE07	Summary of Eye Disorder Events (CTCAE) with Dose Delays by Preferred Term and Maximum Grade		SAC [2]
3.1247 1	Full Safety	Programming note	Summary of Ocular Symptoms and Visual Acuity Change (GSK Scale) by Worst Grade of Keratopathy	Refer regqry_2020_10	SAC [2]
3.1247 2	Full Safety	Programming note	Summary of Ocular Symptoms and Visual Acuity Change (GSK Scale) by Worst Grade of Corneal Events (GSK Scale)	Refer regqry_2020_10	SAC [2]
3.1247 3	Full Safety	Programming note	Summary of Ocular Symptoms and Visual Acuity Change (>=2 lines in Better Eye) by Worst Grade of Corneal Exam Finding	Refer regqry_2020_10	SAC [2]
3.1248 0	Full Safety	OAE07	Summary of Eye Disorder Events (CTCAE) Leading to Dose Delays by Preferred Term and Maximum Grade	Refer regqry_2020_04	SAC [2]
3.1249 0	Full Safety	Programming note	Summary of Subjects with Dose Delay due to Eye Disorder Events (CTCAE) at the Time of Data Cutoff	Refer regqry_2020_04	SAC [2]
3.1273 1	Full Safety	Programming note	Summary of Vision Blurred, and Dry Eye by Preferred Term in Subjects with Keratopathy	Refer regqry_2020_08	SAC [2]
3.1273 5	Full Safety	Programming note	Summary of Vision Blurred, and Dry Eye by Preferred Term and Maximum Grade in Subjects with Keratopathy	Refer regqry_2020_08	SAC [2]
3.12737	Full Safety	Programming note	Summary of Ocular Symptoms (CTCAE) by Preferred Term and Maximum Grade in Subjects with Keratopathy	Refer regqry_2020_10	SAC [2]

CONFIDENTIAL

205678

Safety: Tables					

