Logistic regression analysis of possible risk factors for developing Corneal Events (GSK Scale)

Variable	OR	95% CI	P-value
3.4 mg/kg vs. 2.5 mg/kg	xx.x	(xx.x, xx.x)	0.xxxx*
Male vs. Female	xx.x	(xx.x, xx.x)	0.xxxx
>= 65 vs. < 65	xx.x	(xx.x, xx.x)	0.xxxx
Race	xx.x	(xx.x, xx.x)	0.xxxx
	xx.x	(xx.x, xx.x)	0.xxxx
	xx.x	(xx.x, xx.x)	0.xxxx
Moderate/Severe vs. None	xx.x	(xx.x, xx.x)	0.xxxx

* p<0.05

Example SAFE_T6
 Protocol: 205678
 Population: Safety

Page 1 of 1
 (Data as of: 24APR2018)

Table x.xxxx

Summary of Change from Baseline in Refraction (Spherical Equivalent)

Timepoints	Eye	Refraction	Treatment Group A (N=xxx)	Treatment group B (N=xxx)
Baseline	Right	Actual	n	xxx
			Mean	x.x
			SD	x.xx
			Median	x.x
			Min	x
			Max	xxx
	Left	Actual	n	xxx
			Mean	x.x
			SD	x.xx
			Median	x.x
			Min	x
			Max	xxx
End of	Right	Change from Baseline	n	xxx
			Mean	x.x
			SD	x.xx
			Median	x.x
			Min	x
			Max	xxx
	Left	Change from Baseline	n	xxx
			Mean	x.x
			SD	x.xx
			Median	x.x
			Min	x
			Max	xxx
	Right	Absolute Change from	n	xxx
			Mean	x.x
			SD	x.xx
			Median	x.x
			Min	x
			Max	xxx
	Right	Absolute Change from	n	xxx
			Mean	x.x
			SD	x.xx
			Median	x.x
			Min	x
			Max	xxx

Last follow-up
 Largest absolute
 Change from
 baseline

Example SAFE_T7

Protocol: 205678
 Population: Safety

Page 1 of 1
 (Data as of: 24APR2018)

Table x.xxxx

Summary for Change from Baseline to Worst Post-Baseline in Schirmer's Test and Tear Break-up Time

Parameter		Statistics	Treatment Group A (N=xxx)	Treatment Group B (N=xxx)		
Schirmer's Test (unit = mm)	Right eye	n	xxx	xxx		
		Mean	x.x	x.x		
		SD	x.xx	x.xx		
		Median	x.x	x.x		
		Min	x	x		
		Max	xxx	xxx		
	Left eye	n	xxx	xxx		
		Mean	x.x	x.x		
		SD	x.xx	x.xx		
		Median	x.x	x.x		
		Min	x	x		
		Max	xxx	xxx		
		Tear Break-up time (unit = sec)	Right eye	n	xxx	xxx
				Mean	x.x	x.x
SD	x.xx			x.xx		
Median	x.x			x.x		
Left eye	Min		x	x		
	Max		xxx	xxx		
	n		xxx	xxx		
	Mean		x.x	x.x		
		SD	x.xx	x.xx		
		Median	x.x	x.x		
		Min	x	x		
		Max	xxx	xxx		

Example SAFE_T8
 Protocol: 205678
 Population: Safety

Table x.xxxx
 Summary of Intraocular Pressure (IOP) \geq 22mm Hg Anytime Postbaseline

		Treatment Group A (N = 342)	Treatment Group B (N = 365)
Right eye	n	342	364
	IOP \geq 22mm Hg Anytime Post-baseline	1 (<1%)	2 (<1%)
Left eye	N	342	364
	IOP \geq 22mm Hg Anytime Post-baseline	1 (<1%)	2 (<1%)
Subject (either eye)	n	342	364
	IOP \geq 22mm Hg Anytime Post-baseline	1 (<1%)	2 (<1%)

Example SAFE_T8a
Protocol: 205678
Population: Safety

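### The stepwise corneal-event regression does not say that the randomized dose arm is kept, and it reports ORs, CIs and p-values as if no selection had taken place

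*SAP*

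**What the plan says.** SAP Section 8.2.3, item 9, gives the purpose: "Logistic regression analysis will be performed to explore possible risk factors for developing corneal Events" of grade 2 or above on the GSK scale. The candidate list opens "In addition to dose arm (3.4 mg/kg vs 2.5 mg/kg), Sex (Male vs Female), Age Group" and race. It adds four ocular factors: history of intraocular surgery, lens status, history of dry eye, and baseline keratopathy in three levels. That makes eight factors and nine parameters. The selection rule follows: "Covariates will be selected using stepwise variable selection with entry and exit criteria of" 0.05. No term is declared fixed, and none is expressly declared removable.

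The output is Table 3.1280 (Section 15.13.8), in the Safety population, which is the frozen-liquid arms, delivered at both the primary and the end-of-study analysis. Shell SAFE_T5 in Appendix 14 has "3.4 mg/kg vs. 2.5 mg/kg" as its first row, then sex, age and race and, as the last row, moderate/severe versus none. Each row has an OR, 95% CI and p-value. The dose row carries a star, explained as p<0.05. The SAP describes no full-model table, no penalized or bootstrap estimate, and no caveat about selection.

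**The concern.** Dose is the one randomized factor in this model, and Section 8 of the SAP allows for the lower dose becoming the selected one after the primary analysis. A programmer who applies the selection sentence literally will let dose leave the model. A table without a dose row can be read as showing no dose effect. A table that keeps dose because it passed a 0.05 test shows an estimate filtered for being large. The printed CI and p-value take no account of that filter.

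The shell adds doubt about what is intended. With exit at 0.05, every retained single-parameter factor has p<0.05 in the final model, so a star at p<0.05 distinguishes nothing. Yet SAFE_T5 shows unstarred rows for sex and age. Such rows fit a full model or terms that are always kept, and the text provides for neither. The programming note for Table 3.1280 does not resolve this: it points to item 9 of Section 8.2.2, which has only six items.

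**Working it through.** The SAP gives no event rate, effect size or power for this regression, so it has no figure of its own to reproduce. The check assumes that dose is a stepwise candidate.

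**Inputs from the SAP**
- Entry and exit at 0.05 (read as two-sided); eight factors, nine parameters (Section 8.2.3).
- Size: "it is estimated that approximately 200 participants", about 100 per arm (Section 3.1.1.1). The check uses 97 and 96, the arm sizes in the header of mock shell SAFE_T22.

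**Assumptions**
- Incidence of grade 2 or above: 30%, 50% or 70% in the lower arm, with differences of 5 to 25 points.
- The seven other factors are independent and have no effect. Binary factors have prevalence 20-50%; baseline keratopathy is about 17% mild and 8% moderate/severe.

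**Step 1: approximate chance that dose is kept.** This is the power of a two-proportion test, Φ((d − 1.96·SE₀)/SE₁). For 50% vs 60%:
- pooled SE₀ = √(0.5497 × 0.4503 × (1/97 + 1/96)) = 0.0716
- SE₁ = √(0.25/97 + 0.24/96) = 0.0713
- power = Φ((0.100 − 0.1404)/0.0713) = 0.285

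Across lower-arm incidences of 30-70%, the formula gives 0.29-0.36 at 10 points, 0.55-0.71 at 15 points and 0.80-0.94 at 20 points.

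**Step 2: simulation.** 2,000 trials per row; score test to enter, Wald test to stay. Mean ORs are geometric means. The true OR follows from the incidences, for example (0.6/0.4)/(0.5/0.5) = 1.50.

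| Incidence | True OR | Dose kept | Mean OR when kept | CI coverage when kept | Full model: mean OR | Full model: coverage |
|---|---|---|---|---|---|---|
| 50% vs 55% | 1.22 | 11.9% | 2.00 | 68.6% | 1.26 | 94.5% |
| 50% vs 60% | 1.50 | 28.1% | 2.14 | 90.9% | 1.53 | 94.6% |
| 50% vs 65% | 1.86 | 57.6% | 2.33 | 94.6% | 1.94 | 94.3% |
| 50% vs 70% | 2.33 | 80.5% | 2.64 | 96.6% | 2.44 | 93.6% |
| 50% vs 75% | 3.00 | 95.5% | 3.23 | 96.5% | 3.26 | 93.9% |
| 30% vs 40% | 1.56 | 31.1% | 2.23 | 91.6% | 1.61 | 95.0% |
| 30% vs 45% | 1.91 | 59.4% | 2.39 | 95.4% | 2.00 | 94.7% |
| 30% vs 50% | 2.33 | 81.8% | 2.64 | 96.9% | 2.47 | 95.0% |
| 70% vs 80% | 1.71 | 34.9% | 2.50 | 91.8% | 1.78 | 95.2% |
| 70% vs 85% | 2.43 | 70.8% | 3.01 | 96.4% | 2.60 | 94.8% |

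**Step 3: reading the table**
- Dropped: 65-88% at differences of 5-10 points; 29-42% at 15 points; 18-20% at 20 points; under 5% at 25 points.
- Excess of the retained OR, at 50% incidence in the lower arm: 2.14/1.50 = 1.43; 2.33/1.86 = 1.25; 2.64/2.33 = 1.13; 3.23/3.00 = 1.08.
- Not all of that excess comes from selection. At a true OR of 3.00 the full model itself averages 3.26, which is ordinary small-sample bias.
- At least one factor with no effect entered in 27-31% of runs, as expected for seven null factors: 1 − 0.95⁷ = 0.30.

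**Step 4: alternatives.** With dose forced in and the rest selected, coverage for dose is 94.2-95.5%. The full model gives 93.6-95.2%.

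**The case against.** A reader might infer that dose will usually be dropped and that its CI is invalid in general. The SAP supports neither. It gives no corneal incidence and no dose effect, so any statement of how often is an assumption. In the simulation dose is kept in most trials from about 15 points upward, and coverage given retention is close to nominal from an OR of about 1.86.

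That dose is open to selection is itself only one reading. The ocular factors are introduced as additions to a first list containing dose, and the selection sentence speaks of covariates. With the dose row and the star in SAFE_T5, this allows a model in which dose is fixed. On that reading dose is neither dropped nor materially biased. This stands, but it means the text must say which is meant.

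Much of the dropping is plain low power: retention at 10 points (28-35%) matches the two-proportion power (29-36%). A full model would return p>0.05 about as often, and quoting only its significant results would inflate them in a similar way. This also stands. What the full model gains is that the dose estimate and its interval are always printed.

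Finally, the regression is exploratory and drives no decision rule. Corneal events are shown by arm in several displays (for example Tables 3.0340, 3.0350, 3.0900 and 3.0910), and exposure-response is left to a separate plan (Section 12.1). That limits the consequence to how this one table is read.

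**Conclusion.** The point holds as a minor one. Item 9 prescribes stepwise selection at 0.05 without stating whether the randomized dose arm is kept. The table reports ORs, CIs and p-values as though the model had been fixed in advance, and the shell suggests a different model from the text. If dose is a candidate, it may be lost when the true difference is modest and overstated when kept: by about 43% at a true OR of 1.5 and by 8-13% at ORs of 2.3-3.0 with 30-50% incidence in the lower arm. The excess is larger at high incidence (3.01 for a true 2.43 at 70% vs 85%). Interval coverage suffers only for small effects. These sizes rest on the assumed incidences, on null and independent covariates, and on arm sizes taken from a mock header. With nine parameters and close to 200 participants, selection brings no evident benefit: in the same simulations the full model had coverage close to nominal.

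**What to change.** For Table 3.1280, replace the selection sentence with one prespecified logistic model containing dose arm and all the other listed factors, and report every OR with its 95% CI whatever its p-value, as SAFE_T5 suggests. State in advance which of intraocular surgery and lens status is kept if they largely overlap, and how sparse keratopathy levels are pooled, so that neither choice depends on the results.

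If stepwise is retained, for example to match the table from the primary analysis, state that dose arm is forced in and add a footnote that the other ORs, CIs and p-values are not adjusted for selection. In either case correct the programming note so that it points to Section 8.2.3.

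The cost is a few sentences and simpler code. The downsides are slightly wider intervals for weak factors and a possible difference from the primary-analysis version of the table, which a footnote can explain.
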